However, managing blood glucose levels during exercise is difficult due to absence of the regulatory mechanisms that ensure stable glycemic conditions in people without diabetes. In people without diabetes, physical activity leads to reduced endogenous insulin secretion and increased glucagon and catecholamine secretion which stimulates hepatic glucose release. This hormonal interplay helps facilitate equilibrium in the rate of intramuscular glucose supply to its increasing demand. In people with T1D, circulating insulin levels cannot be physiologically downregulated and the counterregulatory glucagon secretion is blunted (5). Consequently, engaging in aerobic exercise often induces low blood glucose levels (hypoglycemia).

Despite the established health benefits conveyed by physical activity for people with T1D (6–10), participation rates remain low, with fear of hypoglycemia, lack of freedom to engage in unplanned activities, and uncertainty in making appropriate adjustments to insulin and nutritional therapy reported as the leading barriers to regular exercise engagement (11,12).

New commercially available artificial pancreas systems, also known as “advanced hybrid-closed-loop” (AHCL) systems, have shown great result concerning improvement of the glycemic target. The AHCL system continuously anticipates insulin needs, adjusts insulin delivery based on circulating glucose levels and help to protect the user from low glucose levels. However, the person with type 1 diabetes utilizing AHCL systems still needs to plan for exercise, i.e. announcing exercise to the algorithm in advance, and may still require conscious action to consume supplementary carbohydrates around exercise to prevent hypoglycemia.

An ongoing project at Steno Diabetes Center Copenhagen with the title Steno780G study is testing the integration of the MiniMed 780G system in people with T1D around exercise. The study is exploring how best to optimize glycemia around physical exercise through the application of different carbohydrates strategies in people with T1D treated with AHCL therapy. However, increased carbohydrate intake prior to, or during, exercise can negate some of the positive effect of exercise on weight management. Hence, alternative preventative or indeed treatment strategies that increase glucose without the associated caloric expense, may prove valuable for many people with T1D.

In recent years, a number of studies have successfully demonstrated that subcutaneous (s.c.) low-dose glucagon can be utilized to effectively treat insulin-induced and exercise-induced mild hypoglycemia in people with T1D (13–15). Likewise, s.c. infusion of low-dose glucagon in dual-hormone AHCL systems has shown promising results in people with T1D (9).

This will be the first feasibility/pilot study to evaluate the use of glucagon provision for **hypoglycemia prevention** during exercise in people with type 1 diabetes using AHCL therapy; the **“HYPO-AVOID”** study. The results of this research may contribute useful data that helps identify glycaemic management strategies that encourage patient safety, and greater exercise participation in people with T1D.

2. Hypothesis

We hypothesize that low-dose glucagon administered s.c. before aerobic exercise is superior to no glucagon regarding glucose control around exercise in people with T1D using AHCL therapy.

3. Study objective

To compare the effect of low-dose glucagon (single 150 µg dose) administered immediately before aerobic exercise versus a control trial without glucagon on glucose responses during and after exercise in individuals with AHCL-treated T1D.

4. Study design

The HYPO-AVOID study consists of a screening visit (visit A) and two additional study visits (visit B and visit C) completed in a sequential order. During study visit B (detailed in section 9), participants will receive s.c. administration of 150 µg glucagon prior to a 45-min moderate intensity continuous exercise session and subsequently continue into a 1-hour post-exercise observation period. During study visit C the exact same procedures will be followed with the omission of glucagon.

5. Subject selection

The HYPO-AVOID study will include individuals with AHCL-treated (Minimed Medtronic 780G) T1D, and the participants will be recruited from the clinic at Steno Diabetes Center Copenhagen.

A written participant information will be handed out along with the brochure: "Forsøgspersoners rettigheder i et sundhedsvidenskabeligt forskningsprojekt".

For people interested in participating in the HYPO-AVOID study, a subsequent consultation will be scheduled and spoken information will be given by the investigator in a quiet environment. The investigator will, in written and spoken words, ensure that the participant is adequately informed about the study rationale and design. The participant will have the opportunity to ask questions and bring a companion to the interview. Before signing the consent form, the participant is given up to seven days to reconsider. Should the participant need further time, a follow-up meeting will be scheduled. The participants are informed that they may, at any time, withdraw their informed consent to participate in the study without this having consequence for their future treatment. The informed consent procedure may be scheduled at the same day as the screening visit (visit A); however, no study-related examinations will be conducted before the informed consent form has been signed.

In case a participant wants additional information about the study before or after giving consent, the sponsor and primary investigator can be contacted. Information details are given in the study information letter.

If the study is prematurely terminated, the investigator will promptly inform the study subjects and assure appropriate follow-up. The investigator will further inform the Regional Scientific Ethics Committee and the Danish Medicines Agency.

5.1 Inclusion criteria

- Age \geq 18 years
- Type 1 diabetes \geq 2 years
- Using the AHCL system MiniMed 780G \geq 4 weeks
- Novorapid use \geq 1 week

5.2 Exclusion criteria

- Allergies to lactose or glucagon
- Known or suspected allergies to glucagon or related products
- History of hypersensitivity or allergic reaction to glucagon or lactose
- Patients with diagnosed pheochromocytoma, insulinoma or gastroparesis
- Concomitant medical or psychological conditions identified through review of medical history, physical examination and clinical laboratory analysis that, according to the investigator's assessment, makes the individual unsuitable for study participation
- Lack of compliance with key study procedures at the discretion of the investigator
- Females of childbearing potential who are pregnant, breast-feeding or intend to become pregnant or are not using adequate contraceptive methods (methods are considered adequate for study enrolment for females: an intrauterine device, hormonal contraception (birth control pills, implant, patch, vaginal ring or injection), a single partner who is sterile or infertile, or sexual abstinence. Contraception is required throughout the study duration. Sterilized or postmenopausal women (>12 months since last period) are not required to use contraception)
- Inability to understand the individual information and to give informed consent

5.3 Withdrawal criteria

- Pregnancy (or desire for pregnancy) during the study
- Lack of compliance to any of the important study procedures in the discretion of the investigator
- Withdrawal on the participant's request will be accepted at any time without further justification

Withdrawal does not affect the person's statutory patient rights.

6. Screening

After having received a written and oral informed consent, participants will complete a screening visit that reviews the inclusion and exclusion criteria.

At the screening visit a urine sample will be analyzed for albumin/creatinine ratio and U-HCG (for women with childbearing potential). A blood sample will be analyzed for Hemoglobin A1c (HbA1c), hemoglobin, c-peptide, creatinine, eGFR, ALAT, potassium, sodium, TSH, cholesterol, triglycerides, VLDL, LDL and HDL. ECG, blood pressure, and heart rate will also be measured. Participants will also perform a Cardiopulmonary Exercise Test (CPET) to volitional exhaustion on a workload controlled cycle ergometer. If the participant has recently undertaken a CPET as part of their inclusion in the previous clinical trial at SDCC and reports having no overt changes to their habitual fitness routine, the data from this will be used. Please refer to appendix 1 for a thorough breakdown of both the CPET and moderate intensity exercise test protocols and procedures.

If the participant is eligible for the study, baseline characteristics will be obtained which include sex, age, race, diabetes duration, duration of insulin pump use, insulin pump settings, duration of Continuous Glucose Monitoring (CGM) use, CGM values from the previous 2 weeks, allergies, medical history incl. diabetes late complications, medications, educational status, occupational status, hypoglycemia awareness status, height, weight, physical activity status. All the data will be registered in the electronic case report form (eCRF) for each study participant.

If participants are not eligible to participate in the study, the results of abnormal tests, including positive pregnancy test, will be reported to the participant.

7. Randomization and blinding

This is a two period, crossover interventional study, in which there will be no randomization or blinding.

8. Pre-study procedures

Participants must refrain from alcohol consumption and strenuous physical exercise 24 hours before the study visit. Participants will also be instructed not to administrate insulin boluses 4 hours prior to the start of the study visit. Conservative administration of glucose tablets prior to study initiation will be allowed to avoid hypoglycemia.

Individuals will be instructed to avoid hypoglycemia (defined as a sensor value and/or finger prick value $< 3.9 \text{ mmol/l}$) 24 hours before each study visit. Hypoglycemia will be avoided by frequently measuring their plasma glucose (PG) and by setting the CGM low alarm to 4.5 mmol/l. If the participant has a low alarm on the CGM, it should always be ensured by Blood Glucose Monitoring (BGM). CGM data for the previous 24 hours will be evaluated on each study day to check for episodes of hypoglycemia. If hypoglycemia ($< 3.0 \text{ mmol/l}$) has been present, the study visit is postponed for at least one day.

9. Study visit procedures

Arrival and preparation:

In-clinic phase:

- Participants will arrive at the research facility at Steno Diabetes Center Copenhagen in the morning following an overnight fast (incl. coffee, medicine and tobacco). Conservative administration of glucose tablets prior to study initiation will be allowed to avoid hypoglycemia.
- A urine HCG test will be performed for all female subjects with childbearing potential. If the test is positive, the primary investigator will inform the subject of the test result and the visit will be cancelled.
- A peripheral venous catheter will be inserted in the antecubital vein to draw blood.
- 15 mins before exercise, the target glucose level will be increased to 8.3 mmol/L in the AHCL system until 15 mins after end of exercise.
- Venous blood glucose sampling will be taken in 15-min intervals from -45 to -15 mins, 5-min intervals from -15 to +60 mins and 15-min intervals from +60 to +105 mins. Samples will be analyzed immediately to determine blood glucose concentrations and later to characterize the metabolomic, hormonal and physiological responses.

Intervention and exercise:

- Immediately before exercise start ($t = 0$), 150 μg s.c. glucagon will be administrated in the abdominal area at visit B. No glucagon will be given at visit C.
- Subsequently, participants will start exercising on an ergocycle with moderate intensity (60% of $\text{VO}_2\text{-max}$, which is available from the CPET) for 45 mins.
- If the participant experiences hypoglycemia (PG $< 3.9 \text{ mmol/l}$) during the exercise session, exercise will be stopped, and 15 g of oral glucose will be provided. The participant will then rest for the remaining time of the exercise period, and afterwards move on to the post-exercise observation period. If the PG has not risen to $> 3.9 \text{ mmol/l}$ after 15 min, another 15 g of oral glucose will be provided. In the unlikely event that the oral glucose consumption should not prove sufficient to

establish euglycemia, an intravenous glucose infusion will be provided. In both cases, the nadir PG level will be carried forward to the end of the observation period.

Post-exercise observation:

- After ending the exercise session, PG will be monitored for another 60 mins before concluding the study visit.
- The participants will consume a standardized low-glycemic index, carbohydrate-based meal (0.75 g carbohydrates per kg body weight) with their usual meal-time insulin dose.
- Following consumption of this meal, participants will be discharged from the laboratory.

The study visit will be stopped in the following circumstances:

- Inability to perform the exercise session.
- Cardiac discomfort.
- Onset of angina or angina-like symptoms.
- Shortness of breath, wheezing, leg cramps, or claudication.
- Signs of poor perfusion: light-headedness, confusion, ataxia, pallor, cyanosis, nausea, or cold and clammy skin.
- Failure of the testing equipment.

Please see figure 2 illustrating the details for visit B

Trial day schematic – 2.5 hr. Laboratory phase				
Phase	Pre-exercise (rest)	Exercise	Post-exercise (rest)	
	 Lab arrival T= -45 min T= -30 min T= -15 min T= 0 min	 MICE " 60 % VO2max 45 mins	T= +45 min T= +60 min T= +75 min T= +105 min	 Lab departure
Blood sampling*	T= -45, -30, -15, 0 min	Every 5 min	T= +45, +60, +75, +105 min	
Glucagon (s.c. 150 µg)	-	T=0	-	
SG target to 8.3	T=-15	-	T=+60**	

Figure 1: Visit B, *PG, lactate and ketone bodies, metabolomics and hormones; ** the sensor glucose (SG) target will return to the initial value. MICE: Moderate intensity continuous exercise. Subcutaneous glucagon injection pertains to visit B only.

10. Study devices

The AHCL system used in this study is the Minimed 780G pump with the Guardian 3 or Guardian 4 sensor and receiver.

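### Glucagon is always given at visit B and control at visit C, so every B–C endpoint mixes the glucagon effect with visit order and cannot answer the superiority hypothesis

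*Combined protocol and SAP*

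**What the plan says.** Section 4 describes a screening visit followed by "two additional study visits (visit B and visit C) completed in a sequential order". Glucagon is given before exercise at visit B; of the other visit it says: "During study visit C the exact same procedures will be followed with the omission of glucagon". Section 9 repeats this ("No glucagon will be given at visit C"), and the figure legend in that section ties the injection to visit B alone. Section 7 states: "This is a two period, crossover interventional study, in which there will be no randomization or blinding".

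The hypothesis in Section 2 is that low-dose glucagon "is superior to no glucagon regarding glucose control around exercise". The primary endpoint in Section 12.1 (time in range, 0 to +105 min) and every secondary endpoint in Section 12.2 are differences between visits B and C. The protocol describes no counterbalancing and no period term, and it states no planned interval between the two visits.

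Section 13 calls the study a proof of concept, gives no power calculation, sets 16 participants on feasibility grounds, and anticipates that at least 10 of them will go on to the control visit, which it describes as run on a sub-group. Section 4 mentions no such restriction.

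**The concern.** A crossover separates treatment from time because some participants receive the treatments in one order and some in the other. Here there is one order only. Anything that differs systematically between a first and a second exercise visit enters the B–C difference with the same standing as glucagon. Possible examples, not taken from the documents, are familiarity with the session, or a change in fitness or pump behaviour over an interval of unstated length.

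An order effect in one direction would look like a glucagon benefit; in the other it would hide a real one. The hypothesis can then be answered only by assuming that the order effect on the glucose response to exercise is negligible, and the trial's own data cannot test that assumption.

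The sub-group raises a smaller, separate matter. If who goes on to visit C is settled after visit B, the pairs available for comparison may not represent the 16 participants who were dosed.

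**Working it through.** **Step 1. Is the glucagon effect identifiable?** For participant *i*, let *a* be the participant level, *τ* the glucagon effect and *π* the order effect (first visit minus second).

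- Visit B (first, glucagon): *a* + *π* + *τ* + error
- Visit C (second, control): *a* + error
- B–C: *τ* + *π* + error

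The mean B–C difference therefore estimates *τ* + *π*. The rank of the model with participant, period and treatment terms confirms this:

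| Design | Columns | Rank | Period–treatment correlation |
|---|---|---|---|
| All B then C, 10 pairs | 12 | 11 | −1.0 |
| All B then C, 16 pairs | 18 | 17 | −1.0 |
| Balanced order, 5/5 | 12 | 12 | 0 |
| Balanced order, 8/8 | 18 | 18 | 0 |

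The fixed order is one rank short at either size. In the balanced design, glucagon minus control has mean *τ* + *π* in one sequence and *τ* − *π* in the other. The average of the two is *τ*.

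**Step 2. How much could it matter?** The plan has no figure to reproduce: it states no test, alpha, SD or effect size. Everything in this step is assumed: a two-sided 5% paired t-test, normal paired differences, and order shifts *δ* expressed in SDs of the paired difference. With no glucagon effect, the rejection probability comes from the non-central t distribution with *n* − 1 degrees of freedom and non-centrality *δ*√*n*.

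| Pairs | Critical t | *δ* | *δ*√*n* | Rejection probability |
|---|---|---|---|---|
| 10 | 2.262 | 0.25 | 0.79 | 0.109 |
| 10 | 2.262 | 0.5 | 1.58 | 0.293 |
| 16 | 2.131 | 0.25 | 1.00 | 0.155 |
| 16 | 2.131 | 0.5 | 2.00 | 0.465 |

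Nearly all these rejections fall on the side of the shift (0.106 of the 0.109 in the first row). The error grows with sample size, as expected of a bias.

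In the other direction, suppose a true effect of 1.0 SD with 10 pairs. Power is 0.803 without an order effect. An opposing shift of 0.25 leaves a net 0.75 SD and power 0.562; a shift of 0.5 leaves 0.5 SD and power 0.293.

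With balanced random order and period fitted (100,000 simulated trials, no glucagon effect), the rejection rate at shifts of 0.25 and 0.5 was 0.050 and 0.049 with 10 pairs, and 0.049 and 0.051 with 16.

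**Step 3. What does fitting period cost?** One degree of freedom. The ratio of 95% interval half-widths is t(8)/t(9) = 2.306/2.262 = 1.019 with 10 pairs and t(14)/t(15) = 2.145/2.131 = 1.006 with 16.

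**Step 4. Who does visit C?** Section 13 anticipates at least 10 of 16, and 10/16 = 62.5%, so up to 6 dosed participants may contribute no B–C difference. No rule says who proceeds or when that is decided. The possible bias is not quantified here, because any figure would rest on an invented selection rule.

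**The case against.** The strongest reply is that this is an openly non-randomised pilot. Section 2 states a hypothesis and does not claim a result. Section 13 offers no power calculation, and the document sets no test, alpha or success criterion. That stands as far as it goes: a reader might infer that the protocol promises a confirmatory demonstration of superiority, and it does not. But the hypothesis is still comparative and directional, every endpoint is the confounded contrast, and calling the study a crossover suggests a protection that it lacks.

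A second reply is that conditions are well controlled. Participants fast and observe 24-hour restrictions on alcohol and strenuous exercise. At screening they "perform a Cardiopulmonary Exercise Test (CPET) to volitional exhaustion on a workload controlled cycle ergometer", or have recently done one in a previous trial, so the ergometer is not new to them. Glucose is read on a laboratory analyser (Section 18). Starting conditions can also be compared between visits: "Venous blood glucose sampling will be taken in 15-min intervals from -45 to -15 mins", and "CGM data for the previous 24 hours will be evaluated on each study day to check for episodes of hypoglycemia". Pump data are uploaded as well. All this makes an order effect less likely or smaller. It does not show that the response to exercise is free of one. Lactate, ketones and hormones sampled during exercise give some evidence on whether the sessions were comparable, but glucagon may itself affect them, so they cannot separate the two effects.

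Third, Section 11.1 does not expect glucagon to act beyond the study day. That addresses carry-over, not period.

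Fourth, the illustrative rates are normal-theory figures. The primary endpoint is a bounded percentage, and Section 9 carries the nadir forward after treated hypoglycaemia, so the rates may not transfer exactly. That is fair; the aliasing does not depend on them.

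**Conclusion.** The point holds. Treatment and visit order are completely aliased at any sample size, and this follows from the design alone. The size of the consequence is unknown, because the documents give no order effect, SD or test. Under the stated assumptions, a shift of 0.25 to 0.5 SD would raise the false-positive rate from 5% to between 11% and 29% with 10 pairs, or between 16% and 46% with 16.

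Three stronger readings are not supported:

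- A reader might infer that B–C is in fact biased. Nothing in the documents shows that an order effect exists or which way it would run.
- A reader might infer that Sections 4 and 13 contradict each other. Section 4 describes both visits without restriction but never says that all participants do visit C. The scope is unclear rather than contradictory.
- A reader might infer that participants will be chosen for visit C on their visit B results. Selection after visit B is possible because no rule is given, but it is not shown. This secondary gap does not carry the weight of the point.

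**What to change.** **If the order can still be changed.** For participants not yet dosed and scheduled for both visits, randomise the order of the glucagon and control visits 1:1 in small blocks. Fix and record before the first visit who is scheduled for both. Include period in the analysis and base the primary comparison on within-participant pairs.

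This needs a protocol amendment and a short allocation list. It adds no visits, because Section 4 makes the two visits identical apart from glucagon. The 95% interval is about 2% wider with 10 pairs. A participant who has control first and does not return gives no glucagon data, and open-label effects remain.

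**If the order can no longer be changed.** Section 20 expected the first visit in June 2022 and the last in March 2024, and the documents do not show whether enrolment has begun. In that case:

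- remove the word superior from the Section 2 hypothesis;
- describe the study in Section 7 as a non-randomised, single-sequence, two-visit comparison;
- report B–C with a confidence interval, as descriptive and inseparable from visit order;
- compare pre-dose glucose, the prior 24 hours of CGM and pump data between visits, and report the B-to-C interval.

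This route costs only wording and reporting and needs no new data.

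**In either case,** state in Sections 4 and 13 who undergoes visit C and how they are, or were, chosen.

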12.2 Secondary endpoints

- Difference in incidence rate of hypoglycemic events ($PG < 3.9 \text{ mmol/l}$) $(0 \text{ min to } +105\text{min})$ between visits B and C
- Difference in time (min) to hypoglycemia ($PG < 3.9 \text{ mmol/l}$) $(0 \text{ min to } +105\text{min})$ between visits B and C
- Difference in percentage of time below target glucose range ($PG < 3.9 \text{ mmol/l}$) $(0 \text{ min to } +105\text{min})$ between visits B and C
- Difference in percentage of time above target glucose range ($PG > 10.0 \text{ mmol/l}$) $(0 \text{ min to } +105\text{min})$ between visits B and C
- Difference in incidence rate of hyperglycemia ($PG > 10.0 \text{ mmol/l}$) $(0 \text{ min to } +105\text{min})$ between visits B and C
- Difference in nadir PG concentration $(0 \text{ min to } +105\text{min})$ between visits B and C
- Difference in peak PG concentration $(0 \text{ min to } +105\text{min})$ between visits B and C
- Difference in incremental peak PG concentration $(0 \text{ min to } +105\text{min})$ between visits B and C
- Difference in mean PG concentration $(0 \text{ min to } +105\text{min})$ between visits B and C
- Difference in PG Area Under the Curve (AUC) $(0 \text{ min to } +105\text{min})$ between visits B and C
- Difference in standard deviation in PG concentrations $(0 \text{ min to } +105\text{min})$ between visits B and C
- Difference in coefficient of variation in PG concentrations $(0 \text{ min to } +105\text{min})$ between visits B and C

13. Statistical considerations

To our knowledge, this is the first study to evaluate the glucose effects of s.c. injection of glucagon around exercise in individuals with AHCL-treated T1D. This is a proof of concept study to assess the use of low-dose glucagon in persons type 1 diabetes performing exercise during treatment with a hybrid closed-loop system with a control arm as a comparator on a sub-group of the full participant cohort. As such, no power calculation has been performed. The sample size of 16 participants has been chosen from a feasibility perspective. It is anticipated that at least 10 of whom will proceed to complete the control arm for comparative purposes in this proof-of concept study.

14. Safety and risk assessment

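### Carrying the nadir PG forward to +105 min after a treated low makes SD and CV reflect the size and timing of the fall before rescue, not glucose variability

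*Combined protocol and SAP*

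**What the plan says.** Section 9 (intervention and exercise) sets the trigger. If PG falls below 3.9 mmol/l during the 45-minute session, "exercise will be stopped, and 15 g of oral glucose will be provided", with repeat oral glucose and then intravenous glucose if needed. It then gives the data rule: "In both cases, the nadir PG level will be carried forward to the end of the observation period".

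Measurement does not stop at the rescue. Section 9 continues: "After ending the exercise session, PG will be monitored for another 60 mins before concluding the study visit". The sampling schedule in its text is "5-min intervals from -15 to +60 mins and 15-min intervals from +60 to +105 mins", which gives 16 samples from 0 to +105 min.

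Section 12.2 lists "Difference in standard deviation in PG concentrations" and "Difference in coefficient of variation in PG concentrations" over that same window, along with percentage of time below range. Section 3 states the objective as the effect of glucagon "on glucose responses during and after exercise in individuals with AHCL-treated T1D". Section 13 describes no analysis method. It neither limits the carry-forward to particular endpoints nor plans an analysis on the measured values.

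**The concern.** Scoring a rescued participant at the nadir for the rest of the visit stops rescue glucose from being credited as good control. That is sensible for an endpoint that counts success or failure minute by minute. SD and CV are not of that kind. A run of identical imputed values has no spread, so what remains in SD and CV is how far PG fell before the rescue and how much of the window had passed by then.

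At stake is the reading of two visit B minus visit C differences. If lows are more frequent without glucagon, as the study hypothesis implies, the rule acts mainly on visit C. It could make that visit look steadier or more variable than it was, depending on where PG started and when the low came. In addition, the post-exercise part of the objective would be imputed for these participants although it was observed. Only about 10 participants are expected to complete both visits, so a few such visits could matter.

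**Working it through.** The plan gives no figure to reproduce: no expected SD, CV, rate of lows or starting PG. The check applies the stated rule to simple curves.

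**From the protocol.** Window 0 to 105 min; a low can trigger the rule between 0 and 45 min; 16 samples at 0, 5, …, 60, 75, 90, 105 min.

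**Assumed.** PG falls linearly from a start G to a nadir L at time T, then stays at L (the carry-forward). Starts from 4.6 to 8 mmol/l are shown, with L = 3.8 or 3.7.

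**Step 1: share of the window made constant.** (105 − T)/105.
- T = 5: 100/105 = 95% (15 of 16 samples equal the nadir).
- T = 45: 60/105 = 57% (7 of 16 samples).

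**Step 2: closed form.** With D = G − L and f = T/105, the time-weighted mean is L + D·f/2 and the variance is D²(f/3 − f²/4). The variance increases in f up to f = 2/3 (T = 70 min), so for a fixed start and nadir SD is lower the earlier the low, throughout the 45-minute trigger window.

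**Step 3: fixed start 7.0 and nadir 3.7, on the 16-sample schedule.**

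| Low at | Carried-forward SD | Carried-forward CV |
|---|---|---|
| 5 min | 0.82 | 21.1% |
| 15 min | 0.97 | 23.7% |
| 30 min | 1.13 | 25.6% |
| 45 min | 1.19 | 25.2% |

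SD rises throughout; CV is nearly flat after about 30 min. For comparison, assume a measured curve that recovers to 7 mmol/l over 40 min and then stays level. SD is then 1.18, 1.16, 1.13 and 1.14 at the same four times. If recovery is to 6, SD runs from 0.91 to 1.01 (first to last time); if to 8, from 1.51 to 1.35.

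**Step 4: direction against a visit without a low.** Low of 3.8 at 10 min, so f = 0.0952 and √(f/3 − f²/4) = 0.1717. The comparator rises 2.0 mmol/l by 30 min and returns to its start at +105, so its SD is 2.0/√12 = 0.58 and its mean is G + 1.

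- G = 4.6: SD 0.8 × 0.1717 = 0.14, mean 3.84, CV 3.6%. Comparator CV 0.577/5.6 = 10.3%.
- G = 7.0: SD 3.2 × 0.1717 = 0.55, mean 3.95, CV 13.9%. Comparator CV 0.577/8.0 = 7.2%.
- G = 8.0: SD 4.2 × 0.1717 = 0.72, mean 4.00, CV 18.0%. Comparator CV 0.577/9.0 = 6.4%.

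The CV reversal is still present at G = 5.5 time-weighted (7.5% against 8.9%) and gone at 6.0 (9.7% against 8.2%). On the 16 samples it is present at 5.0 (8.3% against 10.7%) and gone at 5.5 (11.7% against 9.9%). SD still reverses at 6.0 on the samples (0.60 against 0.65) and narrowly at 7.0 time-weighted (0.55 against 0.58). Neither measure reverses at 8.0.

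**Step 5: a later low.** From 7.0 to 3.8 at 40 min, carried-forward CV is 21.9% time-weighted. On an assumed curve recovering to 6.0 over 30 min it is 14.5% if recovery starts at once, or about 18% if PG stays at the nadir for 15 min first.

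**Step 6: time below range.** In these examples PG crosses 3.9 about 1.25 min before the nadir.
- Carried forward, low at 10 min from 4.6: (95 + 1.25)/105 = 92%.
- Carried forward, low at 40 min from 7.0: (65 + 1.25)/105 = 63%.
- Measured, immediate recovery to 6.0 over 30 min: PG needs 0.1/(2.2/30) = 1.36 min to pass 3.9, so (1.25 + 1.36)/105 = about 2%.
- Measured, 15 min at the nadir first: (1.25 + 15 + 1.36)/105 = about 17%.

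On the sample schedule the carried-forward values are 14/16 = 88% and 8/16 = 50%. The measured values are 1/16 = 6% and 4/16 = 25%.

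**The case against.** The strongest reply is that the rule exists to stop rescue glucose being counted as control, and that it does this job for time in range. That stands. It extends to time below range, because after a carried-forward low the one loses exactly what the other gains. It would be inconsistent to accept the rule for the first and reject it for the second, so the request there is only for a label and a measured companion figure.

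A reader might infer that the earliest lows always score as the most stable glucose. The calculations do not support this. The ordering holds for a similar start and nadir, or a similar rate of fall. On the sample schedule, a fall from 10 to 3.7 in 10 min gives SD 1.71, while a fall from 5 to 3.8 in 45 min gives 0.43. On the sparser post-exercise schedule in the visit figure, the CV ordering can even reverse for high starts (from 10: 41.8% for a low at 5 min, 37.5% at 45 min).

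A reader might also infer that a glucagon visit would look about three times as variable as a control visit with an early low. That comes from a start of 4.6, only 0.8 above the assumed nadir. The protocol gives no starting PG, and the reversal has gone by 8.0. Nor does it give a rate of lows: more lows at visit C is the hypothesis, not a documented figure.

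The 2% measured time below range is a best case, since Section 9 itself provides for PG that has not recovered after 15 min. Finally, measured SD and CV are not clean either, because they contain the rebound after rescue. That is a real cost, but those values were at least observed.

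**Conclusion.** The point holds for SD and CV. As written, the rule covers them, and for any visit with a treated low during exercise it makes 57% to 95% of the window a constant. That share depends only on the protocol's own timings. The resulting values describe the fall before rescue rather than variability over 0 to +105 min, and the direction of the effect on the B minus C difference varies with starting PG and timing. The SD, CV and time-below-range figures rest on assumed linear curves and should be read as illustrations over a range, not predictions.

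For time below range the point is narrower. The carried-forward version is an acceptable composite, but it is not exposure: about 63–92% time-weighted in the examples, against about 2–17% if measured.

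The documents do not support reading this as a flaw in the primary endpoint, or as a bias of known direction for or against glucagon. Section 9 states the carry-forward for lows during exercise, and nothing here depends on how lows treated afterwards are handled. Only secondary endpoints of an unpowered proof-of-concept study are affected, so this should be corrected but does not undermine the design.

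**What to change.** In Sections 9 and 12.2:

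- Keep the carry-forward for time in range and time below range. Label the latter a composite score of being low or rescued, and report time below range from measured PG beside it.
- State that the carry-forward does not apply to SD and CV. Compute both from measured PG over 0 to +105 min.
- Add a sensitivity analysis of SD and CV over 0 to first rescue (or to +105 min where there was none).

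The cost is wording. No extra samples are needed because PG is already measured after rescue, and no clinical procedure changes. There are two downsides to state openly: measured SD and CV include the rescue rebound, and the truncated window will differ in length between a participant's two visits. There will also be two versions of time below range to report. The scope should be fixed before the data are examined, because visits are unblinded and a later choice would be open to challenge.
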